7.1 Sample Size Determination

The *primary study endpoint* is to determine the efficacy of a single intra-operative injection of BTX-A in the pectoralis major muscle on pain and physical well-being in women undergoing tissue expansions following mastectomy and immediate tissue expander breast reconstruction.

Secondary study endpoints include:

- 1) The initial percent volume expansion (defined as initial intraoperative fill volume divided by manufacturer recommended total tissue expander volume);
- 2) The rate of tissue expansion between the BTX-A groups and the placebo and control groups, with or without the use of ADM;
- 3) Rate of reconstructive failure (tissue expander removal for reasons such as infection or uncontrolled pain).

The *primary safety endpoints* of this study is the incidence of side effects attributable to the injection of BTX-A at doses of 100 units and 200 units, in women undergoing immediate post-mastectomy breast reconstruction with tissue expander(s).

Power and Sample Size: The only available preliminary data for the effect of BTX-A use on pain during initial tissue expansion were obtained from Layeeque et al, *Annals of Surgery* 2004. In this retrospective study, pain was scored using a visual analog scale ranging from 0 to 10, with higher scores indicating increased pain. Layeeque et al reported a mean \pm standard deviation (SD) pain score during initial tissue expansion of 1.95 ± 1.88 for the BTX-A group compared with 5.61 ± 2.77 for the non- BTX-A group.

Sample size estimates were obtained assuming 80% power and a significance level of 0.05 for a two-sample t-test to test the effects of BTX-A use on pain during initial tissue expansion. The table below (entitled Sample Size Estimates) summarizes the sample size needed in each group to achieve approximately 80% power. We calculated the sample sizes needed to detect a 50% decrease in the mean pain scores (assuming mean pain scores for the BTX-A and non-BTX-A groups of 2.0 and 4.0) and a 25% decrease in mean pain scores (assuming mean pain scores for the BTX-A and non-BTX-A groups of 3.0 and 4.0). Sample sizes were calculated assuming low, moderate, and high SDs of 2.0, 2.5, and 3.0, respectively. For example, if mean pain scores for the BTX-A and non-BTX-A groups

were 3.0 and 4.0, respectively, with a moderate SD of 2.5, 100 patients in each group, for a total of 200, would be required to detect this difference as statistically significant.

In order to minimize cost while still maintaining scientific integrity, our goal is to accrue up to 134 patients in order to obtain 128 complete data sets (64 patients per study arm). If the accrual rate was slower than anticipated, we would extend the enrollment period and continue to accrue patients until sample size requirements were met. If the required number of enrolled subjects was not met for any reason, we would end the study and analyze the data using the same techniques. An appropriate cautionary statement would be added to the discussion section of any publication.

SAMPLE SIZE ESTIMATES

BTX-A	Mean Pain	SD	N per Group
No	4.0	2.0	17
Yes	2.0		
No	4.0		64
Yes	3.0		
No	4.0	2.5	26
Yes	2.0		
No	4.0		100
Yes	3.0		
No	4.0	3.0	37
Yes	2.0		
No	4.0		143
Yes	3.0		

7.2 Statistical Methods**Descriptive Statistics:**

Demographic and medical characteristics will be analyzed for all enrolled subjects. Descriptive statistics will be calculated for all baseline variables. Univariate descriptive statistics and frequency distributions will be calculated, as appropriate for all variables. Baseline values for demographic, clinical, and outcome variables (primary and secondary) will be tabulated separately for the treatment groups. These analyses will help identify whether the randomization was successful in equalizing distributions of these prognostic variables across treatment groups or if confounding variables need to be included as covariates in sensitivity analyses. Putative prognostic variables that will be investigated through these descriptive analyses include variables such as age, body mass index, smoking status, diabetes mellitus, coronary artery disease, hypertension, clinical breast cancer stage, mastectomy weight, initial percent volume expansion (defined as initial intraoperative fill volume divided by manufacturer recommended total tissue expander volume), sentinel lymph node biopsy, axillary dissection, adjuvant therapy factors (e.g., previous and postoperative chemotherapy and radiation), operative time, ADM use.

Handling of Missing Data

Handling of missing data will be done in a number of ways including complete-case analysis and multiple imputations via nearest neighbor, mean value, last value, and zero value carried forward

approaches. Multiple approaches are used so that the sensitivity of results to alteration in multiple imputational assumptions may be assessed.

Primary Hypotheses:

- Pain scores will be at least 25% less, in those who received BTX-A, during the immediate post-operative period compared to those who received saline injections
- Pain scores will be at least 25% less, in those who received BTX-A, during the period of tissue expansion, compared to those who received saline injections
- Physical Well-Being scores during tissue expansion will be higher in those who received BTX-A compared to those who received saline injections

There are two primary outcomes: pain intensity measured by the NPIS, and physical well-being using the BREAST-Q®. The primary analysis will be performed during the post-operative period and during the expansion phase. Outcome variables will be summarized with frequency counts and percentages or means, standard deviations, medians, and ranges, as appropriate. The mean, median, standard deviation, and range of each variable and its change from baseline, measured on a continuous scale, will be presented by treatment and visit. Frequency tables will be provided for categorical variables by treatment and visit. Any differences among the study groups will be evaluated using two-sample t, Wilcoxon rank sum, Pearson's chi-square, or Fisher's exact tests.

Secondary Hypotheses:

- 1) There will be no difference in the initial percent volume expansion between groups (defined as initial intraoperative fill volume divided by manufacturer recommended total tissue expander volume);
- 2) The rate of tissue expansion will be higher in the BTX-A groups compared to the placebo group, with or without the use of ADM;
- 3) There will be no difference in the rate of reconstructive failure (tissue expander removal for reasons such as infection or uncontrolled pain).

The volume of tissue expansion anticipated and the rate of tissue expansion between the BTX-A groups and the placebo and control groups will be calculated both as an absolute value as well as a percentage. It is hypothesized that the use of BTX-A may increase the rate of tissue expansion, which may lead to fewer postoperative tissue expansion visits. This will allow measurement of effect size between the intervention and the placebo groups. Two-sample t and Wilcoxon rank sum tests will be used for the secondary analyses.

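### Three primary hypotheses have no testing order, alpha split or win rule, and each plausible reading loses either control of false claims of benefit or the stated 80% power

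*Combined protocol and SAP*

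**What the plan says.** Section 7.2 gives three primary hypotheses:

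1. "Pain scores will be at least 25% less, in those who received BTX-A, during the immediate post-operative period";
2. "Pain scores will be at least 25% less, in those who received BTX-A, during the period of tissue expansion";
3. "Physical Well-Being scores during tissue expansion will be higher in those who received BTX-A".

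The same section counts the outcomes differently: "There are two primary outcomes: pain intensity measured by the NPIS, and physical well-being". It places the primary analysis in both the post-operative period and the expansion phase. Its decision machinery is a list of tests: "Any differences among the study groups will be evaluated using two-sample t, Wilcoxon rank sum", followed by two tests for categorical data.

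Section 7.1 states its error rate and 80% power for one comparison, at a "significance level of 0.05 for a two-sample t-test to test the effects of BTX-A use on pain during initial tissue expansion". The chosen 64 per arm is the table row for a "25% decrease in mean pain scores (assuming mean pain scores for the BTX-A and non-BTX-A groups of 3.0 and 4.0" respectively, with SD 2.0, which the section calls low. Its other SDs are 2.5 (moderate) and 3.0 (high).

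The hypothesis in Section 2 and the endpoint in Sections 3.2 and 7.1 join pain and physical well-being with the word 'and'. No section gives an order, an alpha split, a multiplicity adjustment or a statement of what makes the trial positive.

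**The concern.** A reader of the final report could not tell from the plan whether one significant result out of three is a success, whether all three are needed, or whether a significant pain result with an observed reduction below 25% counts. These rules have different error rates and different power, and choosing among them after seeing results would be open to challenge.

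The single alpha and power statement does not settle the matter. It covers the initial expansion, which is narrower than the expansion-period hypothesis, and it says nothing about post-operative pain or physical well-being. The trial is labelled Phase 3 and Section 1.1 expects it to supply evidence of use to the FDA, whereas Section 2 calls its results preliminary. Either use needs one stated rule.

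**Working it through.** **Inputs from the protocol.** Two-sample t-test, alpha 0.05, 64 per arm, means 4.0 and 3.0, SD 2.0, 2.5 or 3.0 (Section 7.1); three primary hypotheses (Section 7.2).

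**Assumptions.** Two-sided testing is inferred, because one-sided 0.05 would give 50 per arm rather than 64. The correlation between the three test statistics is not given; I use an equal value for each pair, from 0 to 0.9.

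**The plan's own figure.** The noncentrality is 1.0 / (2.0 × √(2/64)) = 2.83. The two-sided t-test then needs 63.8 per arm for 80% power, so 64, with power 80.1%. All six rows of the sample-size table reproduce.

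**Reading (a): any one may win, and 25% is only the sizing effect.** With independent tests, the false-benefit rate is 1 − 0.975³ = 7.3%. Correlated values come from simulating three equicorrelated normal statistics with critical value 1.96.

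| Correlation | 0 | 0.5 | 0.7 | 0.9 |
|---|---|---|---|---|
| False claim of benefit (one test: 2.5%) | 7.3% | 6.3% | 5.5% | 4.2% |

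**Reading (b): any one may win, but pain also needs an observed reduction of at least 25%.** The extra condition is 0.75 × control mean − BTX-A mean ≥ 0. The standard error of this quantity is SD × √((0.75² + 1)/64) = 0.156 × SD.

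- *No effect, both means 4.0.* The expected value is −1.0. At SD 2.0 the standard error is 0.3125, so the condition is met with probability P(Z > 3.2) = 0.0007. Physical well-being has no 25% threshold and keeps 2.5%. At correlation 0 the any-of-three rate is 1 − 0.9993² × 0.975 = 2.6%. Over correlations 0 to 0.9 it is 2.6-2.5% at SD 2.0, 3.5-2.6% at SD 2.5 and 5.6-3.4% at SD 3.0.
- *Sized effect, means 3.0 and 4.0.* The expected value is exactly 0, so the condition is met half the time. Requiring p < 0.05 as well gives power of 50%, 50% and 45% at SD 2.0, 2.5 and 3.0, against 80%, 61% and 46% for p < 0.05 alone.

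**Reading (c): all three must win.** Alpha is not inflated. If each test has 80% power, joint power is 0.8³ = 51% at correlation 0, then 61%, 66% and 72% at 0.5, 0.7 and 0.9. The protocol supports 80% for one test only, and only at SD 2.0.

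**Power of the first test under the proposed sequence, 64 per arm, difference 1.0.** For a patient's mean over k visits, SD_k = SD × √((1 + (k − 1)ρ)/k), with within-patient correlation ρ assumed 0.5-0.9 and the same difference at every visit. For example, at SD 2.0, k = 2 and ρ = 0.9 give SD_k = 1.95 and power 82%; k = 7 and ρ = 0.5 give 1.51 and 96%.

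| Per-visit SD | One visit | Mean of 2-7 visits |
|---|---|---|
| 2.0 | 80% | 82-96% |
| 2.5 | 61% | 64-84% |
| 3.0 | 46% | 48-70% |

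The upper limit of seven visits is borrowed from the off-site questionnaire packet in Section 5.5; it is not a stated visit count.

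**The case against.** The best defence is that the plan's own wording points away from inflation. Both pain hypotheses carry the 25% threshold; read as a success criterion, it leaves almost no excess false-benefit rate at SD 2.0. The word 'and' in Sections 2, 3.2 and 7.1 favours requiring success on both outcomes, and then there is no inflation at all. Both points stand as far as they go. A reader might infer that the plan raises the false-claim rate to 4-7% outright; the documents do not support that, because they never say that one success is enough and they give no correlations. But neither defence is written as a decision rule, and adopting either one gives up the 80% power.

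A reader might also infer that the interim analysis adds inflation through an unadjusted efficacy look. The text is contradictory rather than clear. Sections 1 and 8.6.2 have the monitoring board assess efficacy at 75 enrolled. Section 8.6.1 has a review after half the target, which is 67 of 134 or 64 of 128; it mentions efficacy but says the patient-reported data are reviewed pooled. Section 8.4 has the interim statistician request un-blinding. Whether the arms are compared is not established, so I count no inflation from this source.

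Finally, leading with expansion pain is a choice, and other valid rules exist. It fits the Section 2 aim, which concerns the expansion period, and the outcome that was sized. An equal three-way alpha split would leave 66% power at 64 per arm and need 86 per arm for 80%.

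**Conclusion.** The concern holds in this form: three primary hypotheses have no rule for what counts as success, and every plausible reading loses a property that the plan appears to have. Reading (a) loses error control (7.3-4.2% against 2.5%). Reading (b) largely keeps it at SD 2.0, less so at SD 3.0, but cuts power for a pain hypothesis to about 50%. Reading (c) keeps alpha and loses joint power (51-72%).

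The absence of a rule is plain from the text. The sizes are scenarios that depend on the assumed correlations, on two-sided testing, on exactly three final tests and, for (c), on 80% power for each. The gap should be closed before any between-arm data are seen, because it cannot be credibly repaired afterwards.

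**What to change.** Amend Section 7.2, with matching wording in Sections 3.2 and 7.1:

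- Name expansion-phase NPIS pain as the first primary hypothesis, at two-sided 0.05. Use one per-patient summary fixed in advance: either the mean over her expansion visits, or the initial expansion visit that was sized. Each patient counts once, which matters because Section 7.2 expects faster expansion under BTX-A, "which may lead to fewer postoperative tissue expansion visits".
- Then test physical well-being during expansion and NPIS at the first post-operative visit in a fixed sequence, each at 0.05 only if the previous test is significant. The sponsor may choose the order of these two, but the amendment must fix it before any between-arm data are seen.
- State that the 25% figure is the sizing effect and not a success criterion.

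The cost is a short amendment submitted to the IRB, and the later hypotheses can be claimed only in sequence. If each has 80% power, the chance of winning the first two is 64-75% over correlations 0 to 0.9. The first test keeps 64 per arm, with the power tabulated above; 80% at one visit holds only at the low SD.

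Separately, reconcile Sections 1, 8.4, 8.6.1 and 8.6.2 on when the interim occurs and whether it reviews pooled or between-arm efficacy data, and state that it makes no between-arm efficacy comparison. If an efficacy stop is wanted, specify its boundary and how the later hypotheses are tested after a stop.

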3.2 Primary Study Endpoints

The primary study endpoint is to determine the efficacy of a single intra-operative injection of BTX-A in the pectoralis major muscle on pain and physical well-being in women undergoing tissue expansions following mastectomy and immediate tissue expander breast reconstruction.

The outcome measures selected to test our working hypothesis and answer our specific aim #1 are a numeric pain intensity scale (NPIS)⁷¹, and the Physical Well-Being scale of the BREAST-Q®: Reconstruction Module. The NPIS is a reliable and valid tool that is widely used as a measure of pain intensity (See Appendix for complete scale). To assess physical well-being, we selected the 16-item Physical Well-Being scale from the BREAST-Q®: Reconstruction Module. The BREAST-Q® is a newly-developed and validated PRO measure designed to measure patients' perception of outcomes following breast surgery.⁷² The Reconstruction Module consists of scales in six domains related to satisfaction and QoL (See Appendix for complete scale). The Physical Well-Being scale has items that relate to issues surrounding chest and upper body symptoms, and how these impact on physical function and participation in activities before and after breast reconstruction. Study participants will answer how often they have experienced each symptom during the previous two-week period, using a 5-point Likert scale (1 – none of the time, 5 – very often). Answers from these questions will be combined to provide a total physical well-being score for each patient at each follow-up visit. Average scores for both study groups will be compared. These two measures will be administered at the pre-operative visit, the first postoperative visit (1-2weeks) and subsequent Plastic Surgery appointments/expansion visits until the end of study is reached. After much consideration, we have made the decision not to ask enrolled subjects to record the amount of oral analgesic medication taken

daily during the course of the study, as this method is often inaccurate due to missing data entries, and would therefore yield unreliable results. Furthermore, the randomization process in this study should ensure a random distribution of patients with different oral analgesics intakes. It was also felt that not recording the amount of oral analgesic medication would reduce the burden of study participants.

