5.5 Subject Compliance Monitoring

To assure adherence to the one-time intraoperative study drug intervention, the study coordinator will review documentation of intraoperative medications. Monitoring adherence of timely questionnaire completion at each tissue expansion visit will also occur. For patients who will undergo tissue expansions at Mayo Clinic, the study coordinator will ensure that the questionnaires have been fully completed by the study participants before they leave the premises.

In some instances, study participants will not return to Mayo Clinic for each tissue expansion visit. The study coordinator will prepare a packet for these women that will include 7 questionnaires and 7 prepaid return envelopes by post. The study participants are to fill out and return one copy of the questionnaire at each tissue expansion visit performed at an outside institution. To maximize the response rate, we will use the methodology recommended by Dillman⁷³. If the questionnaire is not returned within one week after the planned tissue expansion visit, the study coordinator will contact the patient, and complete the questionnaire by phone. A telephone script will be used for this purpose. If the patient cannot be reached by phone, a reminder will be sent along with one additional copy of the questionnaire.

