5.9.4 Return or Destruction of Study Drug

At the completion of the study, there will be a final reconciliation of drug shipped, drug consumed, and drug remaining. This reconciliation will be logged on the drug reconciliation form, signed and dated. Any discrepancies noted will be documented and investigated, prior to return or destruction of unused study drug. Drug destroyed on site will be documented in the study files.

6 Study Procedures

TABLE OF VISITS:

	Research activity	Subject activity
Preoperative evaluation/Surgical listing appointment	Study Coordinator (SC) reviews the study with eligible patients and obtains informed consent	Complete the BREAST-Q and Numeric Pain Intensity Scale
Surgery	Randomization by site specific research pharmacy and intra-operative injection of study drug by plastic surgeon	•
First post-operative visit: • Week 1- 2	SC facilitates completion of questionnaire and assesses for adverse events	Complete the BREAST-Q and Numeric Pain Intensity Scale
Subsequent Plastic Surgery Appointments/Expansion Visits • Beginning at week 2-3 and intervals thereafter as determined by the plastic surgeon	SC facilitates completion of questionnaire and assesses for adverse events	Complete the BREAST-Q and Numeric Pain Intensity Scale
• End of Study • The last plastic surgery appointment prior to removal of the TE, or the date of TE removal (whichever occurs last within the 4 month postoperative period)		

Tissue expander placement: The surgical procedure for submuscular placement of the tissue expander will be performed in the usual manner by each participating plastic surgeon.

BTX-A Injection Protocol: see Section 5.4

Outcome Assessment: The outcome measures selected to test our working hypothesis and answer our specific aim #1 are a numeric pain intensity scale (NPIS)⁷¹, and the Physical Well-Being scale of the BREAST-Q®: Reconstruction Module. These two measures will be administered to study participants at the pre-operative visit, the first postoperative visit (1-2 weeks), and subsequent Plastic Surgery appointments/expansion visits until the end of the study is reached.

7 Statistical Plan

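### Section 7.2 does not define each woman's expansion-phase value for two primary hypotheses, and no primary test is stated to use the baseline score already collected

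*Combined protocol and SAP*

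**What the plan says.** Section 7.2 lists three primary hypotheses. The first concerns pain in the immediate postoperative period and is adequately located, because the Table of Visits in section 6 has one visit there, at week 1-2. The other two concern expansion: "Pain scores will be at least 25% less, in those who received BTX-A, during the period of tissue expansion" and "Physical Well-Being scores during tissue expansion will be higher in those who received BTX-A".

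NPIS and BREAST-Q are completed before surgery, at week 1-2 and at every later plastic surgery or expansion visit (sections 3.2 and 6). Expansion visits begin at week 2-3, with "intervals thereafter as determined by the plastic surgeon". Follow-up ends at the last appointment before expander removal or at removal, "whichever occurs last within the 4 month postoperative period". Section 5.5 gives women who are expanded elsewhere "a packet for these women that will include 7 questionnaires and 7 prepaid return envelopes by post", which suggests up to about seven expansion-phase scores per woman. Section 3.2 says the BREAST-Q answers will "provide a total physical well-being score for each patient at each follow-up visit".

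For analysis, section 7.2 says: "Any differences among the study groups will be evaluated using two-sample t, Wilcoxon rank sum", followed by two tests for categorical data. Change from baseline is to be presented by treatment and visit. Covariates appear only where descriptive tables would show "if confounding variables need to be included as covariates in sensitivity analyses". Section 7.2 also hypothesises that BTX-A may speed expansion and so lead to fewer visits.

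**The concern.** A two-sample t or Wilcoxon test needs one value per woman. During expansion a woman has several scores, and the plan does not say whether her value is the first, last, mean or worst of them, or whether each visit is tested separately. These choices answer different questions and have different variances.

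Timing adds to the problem. Surgeons set the visit intervals, and the plan expects that treatment may change the number of visits. A last-visit, worst-score or all-visit summary, or a comparison by visit number, could therefore compare the arms at different times after surgery.

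The pre-operative score is collected from every woman but is given no stated role in a primary test. Adjusting for it is a nearly cost-free way to gain precision, and the planned size has little to spare: 64 per arm matches the lowest of the three SDs in section 7.1.

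**Working it through.** **Inputs from the plan.** Section 7.1: mean pain 4.0 against 3.0 (difference 1.0); SD 2.0, 2.5 or 3.0; 80% power; significance level 0.05 (taken as two-sided); two-sample t-test; 64 per arm.

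**Assumed inputs.** The documents give no correlations. I take a baseline-to-follow-up correlation r of 0.1 to 0.5 and a within-patient correlation rho between visits of 0.5 to 0.8. The low end of r is plausible because section 4.2 excludes documented chronic pain, so pre-operative NPIS may lie near zero for many women. The number of scores averaged, k = 2.76, is what a four-week window yields with visits every 1 to 2 weeks, which is also an assumption.

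**Step 1: the plan's own figure.** For a standardised difference of 1.0/2.0 = 0.5, the exact t-based solution is 63.77, rounded up to 64 per arm, as stated. At SD 2.5 it is 99.08, rounded up to 100, also as stated. The table in section 7.1 is correct. It applies to one unadjusted value per woman.

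**Step 2: one visit, unadjusted, 64 per arm.** Power is 80% at SD 2.0 and 61% at SD 2.5.

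**Step 3: one visit, ANCOVA on baseline.** Residual SD = SD × √(1 − r²), with 2 × 64 − 3 = 125 degrees of freedom. For example, SD 2.0 and r 0.3 give 2.0 × √0.91 = 1.908.

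| r | Power, SD 2.0 | Power, SD 2.5 |
|---|---|---|
| 0.1 | 81% | 62% |
| 0.2 | 82% | 63% |
| 0.3 | 84% | 65% |
| 0.5 | 90% | 74% |

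**Step 4: change from baseline, if section 7.2 were read as testing it.** SD of change = SD × √(2(1 − r)). At r 0.3 this is 2.0 × √1.4 = 2.366 and power is 66%. At r 0.5 it is 2.0 and power is 80%. Below r 0.5, a change score does worse than ignoring baseline.

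**Step 5: unadjusted mean of k = 2.76 scores.** SD of the mean = SD × √((1 + (k − 1)rho)/k). For SD 2.0 and rho 0.5: 2.0 × √(1.88/2.76) = 1.651.

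| rho | 1.0 point, SD 2.0 | 1.0 point, SD 2.5 | 0.8 points, SD 2.0 | 0.8 points, SD 2.5 |
|---|---|---|---|---|
| 0.5 | 93% | 78% | 78% | 59% |
| 0.6 | 90% | 74% | 74% | 55% |
| 0.8 | 85% | 67% | 67% | 49% |

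The 0.8-point columns show what happens if the effect averaged over the window is smaller than the effect at initial expansion. The gain over the single-visit figures in step 2 (80% and 61%, at 1.0 point) then disappears.

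**BREAST-Q.** The documents give no SD or target difference, so no size can be given.

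**The case against.** The plan is not silent. Section 7.1 sizes the trial on pain during initial tissue expansion, section 3.2 says average scores of the two groups will be compared, and section 7.2 presents results by visit. Together these could be read as per-visit comparisons anchored on the first expansion. That reading remains incomplete: the phrase in 7.1 is a sizing assumption for pain only, 7.2 does not carry it forward, and the sentence in 3.2 names no visit. Change from baseline stands in the same paragraph as the tests, so testing it is not excluded, but no test is tied to it.

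Baseline adjustment may add little. At r 0.1 to 0.2 it adds one or two percentage points of power. This stands, and most of any larger gain comes from averaging visits. That gain depends on a constant effect, and section 7.1 supports 1.0 point for initial expansion only.

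A prescribed window has its own hazards. One that opens at week 3 could miss a first expansion in week 2, which is the score used for sizing. BREAST-Q asks about the previous two weeks (section 3.2), so an early form largely describes recovery from surgery. The remedy has to respect both.

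A reader might also infer that the open choice makes the trial prone to false positives. The documents do not say that several summaries will be tried, and section 5.3 keeps those who analyse the data blinded, so no particular error rate follows from the text.

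**Conclusion.** The point holds as a gap in definition and a missed, nearly cost-free gain in precision. Two of three primary hypotheses lack a defined per-woman value, and no primary test is stated to use baseline. At SD 2.0, baseline adjustment raises single-visit power from 80% to between 81 and 90% for assumed r of 0.1 to 0.5. At SD 2.5 it raises it from 61% to between 62 and 74%. Averaging visits could add more, but only if the effect persists over the window.

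Three stronger readings are not supported. An unadjusted comparison at one fixed time is not invalid. Misaligned visit timing does not favour a known arm, because the documents give no pain trend over time; if pain falls and BTX-A shortens expansion, an all-visit mean would run against BTX-A. Nor do the documents make a mixed model over fixed weeks necessary. The change should be made, but the trial does not fail without it.

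**What to change.** In section 7.2:

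- **Early pain.** Analyse the week 1-2 NPIS by ANCOVA with arm and baseline NPIS.
- **Expansion-phase value.** Before unblinding, fix one contrast for NPIS and one for BREAST-Q, defined by time since surgery and not by visit number. One option is each woman's mean score over a window that opens at her first expansion visit or at week 2, with its end set from blinded visit dates so that nearly all women have a score. Count a BREAST-Q form only if its two-week recall falls mainly within expansion.
- **Dating.** Date each score by the visit it refers to, because section 5.5 allows forms to be completed by telephone or post more than a week later.
- **Primary comparison.** Use ANCOVA on that value with the same scale's pre-operative score as covariate.
- **Supportive analyses.** Keep the t and Wilcoxon tests, add a mixed model using time since surgery, and repeat the primary analysis over the whole expansion period to 4 months.

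The cost is SAP wording, a visit date for each questionnaire including mailed ones, and a primary contrast that may not cover the whole expansion period. No added patients or visits are needed. Adjustment does not guarantee freedom from bias if pain itself drives visit timing.

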3.3 Secondary Study Endpoints

Secondary study endpoints will include:

- 1) The initial percent volume expansion (defined as initial intraoperative fill volume divided by manufacturer recommended total tissue expander volume);
- 2) The rate of tissue expansion between the BTX-A group and the placebo group, with or without the use of ADM;
- 3) Rate of reconstructive failure (tissue expander removal for any reasons, such as infection or uncontrolled pain).

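### Section 7.2 hypothesises no difference in reconstructive failure but plans only tests of difference, with no margin, interval or power, so a non-significant result could not support it

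*Combined protocol and SAP*

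**What the plan says.** Section 3.3 lists as the third secondary endpoint "Rate of reconstructive failure (tissue expander removal for any reasons, such as infection or uncontrolled pain". For each woman this is a yes/no outcome. Under Secondary Hypotheses, section 7.2 states that "There will be no difference in the rate of reconstructive failure". It says the same of a second endpoint: "There will be no difference in the initial percent volume expansion between groups".

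The paragraph after those hypotheses deals with the volume and rate of expansion and ends: "Two-sample t and Wilcoxon rank sum tests will be used for the secondary analyses". Earlier in 7.2, a general sentence on group comparisons also lists Pearson's chi-square and Fisher's exact tests, and the Précis gives the same four tests. Section 7.2 also promises frequency tables for categorical variables by treatment.

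No section gives an equivalence or non-inferiority margin, an expected failure rate, a confidence interval for the difference in failure, or a power statement for it. The sample size in 7.1 rests on pain alone.

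**The concern.** A hypothesis that two groups do not differ needs an analysis that can bound the difference. A test of difference that fails to reject leaves open every difference the trial was too small to see. With no margin and no planned interval, the only result the plan offers for judging this hypothesis is a p-value above 0.05.

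Reconstructive failure is the harm-related secondary endpoint, since its definition includes removal for infection or uncontrolled pain. Section 2 expects the benefit of treatment to outweigh adverse events, and a finding of no difference in expander loss would feed that claim. The numerical stopping rule in 8.5 covers surgical site infection, not expander loss.

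The two lists of tests also disagree. Read literally, the sentence on secondary analyses leaves out the usual tests for a yes/no endpoint.

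**Working it through.** **1. The plan's own figure.** Inputs from 7.1: "assuming 80% power and a significance level of 0.05 for a two-sample t-test"; a 25% reduction, "assuming mean pain scores for the BTX-A and non-BTX-A groups of 3.0 and 4.0"; and the lowest of "low, moderate, and high SDs of 2.0, 2.5, and 3.0". The standardised difference is 1.0/2.0 = 0.5. The normal approximation gives n = 2(1.960 + 0.842)²/0.5² = 62.8, so 63 per arm. The noncentral-t solution is 63.77, so 64. The stated 64 is reproduced with a two-sided test. The target is to "accrue up to 134 patients in order to obtain 128 complete data sets (64 patients per study arm". This sizing says nothing about failure.

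**2. Power for a doubling of failure.** The control rates are assumptions. With a and b failures out of 64 in the two arms,

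power = Σₐ Σ_b Bin(a; 64, p) · Bin(b; 64, 2p) · 1[p-value(a, b) ≤ 0.05],

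summed over all 65 × 65 outcomes, two-sided:

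| Assumed rates | Chi-square | t on 0/1 data | Wilcoxon | Fisher |
|---|---|---|---|---|
| 5% v 10% | 19% | 19% | 19% | 10% |
| 10% v 20% | 35% | 35% | 35% | 27% |
| 15% v 30% | 53% | 53% | 53% | 45% |
| 20% v 40% | 71% | 71% | 70% | 63% |
| 25% v 50% | 85% | 85% | 85% | 80% |

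At 10% v 20%, a true doubling is non-significant in about 65% (chi-square) to 73% (Fisher) of trials.

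**3. Size needed for 80% power.** n = [1.960·√(2p̄q̄) + 0.842·√(p₁q₁ + p₂q₂)]² / (p₂ − p₁)². For 10% v 20%: (1.960·√0.255 + 0.842·√0.25)²/0.01 = 199 per arm. For 5% v 10% it is 435, for 15% v 30% it is 121, and for 20% v 40% it is 82.

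**4. A possible result.** Take 6/64 v 12/64, an observed doubling with a difference of 9.4 points.
- Chi-square: pooled rate 18/128 = 0.1406; SE = √(0.1406 × 0.8594 × 2/64) = 0.0615; z = 0.0938/0.0615 = 1.53; p = 0.13. The t-test also gives 0.13, and Fisher 0.20.
- Newcombe 95% CI: the Wilson intervals are 4.4% to 19.0% and 11.1% to 30.0%. Lower limit 9.4 − √[(18.75 − 11.06)² + (18.98 − 9.38)²] = −2.9 points. Upper limit 9.4 + √[(29.97 − 18.75)² + (9.38 − 4.37)²] = +21.7 points.
- t-interval for the same data: 9.4 ± 1.979 × 6.14 = −2.8 to +21.5 points.

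This result is compatible with the stated hypothesis, and also with an increase of more than 20 points. Even 9 v 18 gives chi-square p = 0.051.

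**5. What an interval or a margin could deliver at 64 per arm.** If both true rates are 10%, the 95% half-width is 1.96·√(2 × 0.10 × 0.90/64) = 10.4 points. For an illustrative 10-point non-inferiority margin with equal true rates p, power = Φ(0.10/√(2p(1 − p)/64) − 1.96), which is 74%, 47%, 35% and 29% for p = 5%, 10%, 15% and 20%.

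**The case against.** Several parts of the case on the other side stand.

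- **No written rule.** A reader might infer that the plan declares equivalence when p exceeds 0.05. No section says so, and the hypotheses can be read as expectations. The inference comes from pairing a no-difference hypothesis with tests of difference only.
- **The choice of test is not the cause.** It is tempting to say that t and Wilcoxon tests would hide a doubling. Step 2 shows otherwise: on 0/1 data they reach nearly the same decisions as chi-square, and Fisher is the less powerful choice. Nor does a t-test rule out an interval for the risk difference. Step 4 gives one, close to Newcombe's.
- **Chi-square and Fisher's exact are in the plan.** They are in the general list, and the t/Wilcoxon sentence closes a paragraph on continuous expansion measures. It may have been meant only for those. It does say the secondary analyses without limit, so the two sentences need reconciling, but this is an inconsistency and not a settled prescription.
- **The rates are assumed.** At 25% v 50%, power is 80% to 85%.
- **Initial percent volume carries little weight.** The same logical gap exists there, but the initial fill is set in the same operation as a blinded injection, 1.5 puts the paralytic action at about 7 to 10 days, and 7.2 also lists the variable as prognostic.
- **A mandatory margin would be debatable.** Step 5 shows that a 10-point margin would often be inconclusive at this size.

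None of this gives the plan a way to support its hypothesis on failure. Frequency tables would show the counts, but no bound on the difference is promised.

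**Conclusion.** The point holds for reconstructive failure. The plan hypothesises no difference, provides only tests of difference, and has no margin, interval or power for the endpoint. Non-significance would be uninformative over much of the plausible range. For a true doubling, power is 19% or less if the control rate is 5% and 35% or less if it is 10%. It does not reach 80% until the control rate is somewhere between 20% and 25%. These figures assume 64 women per arm, one outcome per woman, a two-sided 5% level and control rates that the documents do not supply.

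The documents do not support saying that the drug raises expander loss, that a doubling is expected, or that the sponsor has committed to reading non-significance as proof. The defect is that nothing in the plan prevents that reading. It should be corrected before analysis, and it does not touch the primary comparison.

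**What to change.** In section 7.2:

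1. Name Pearson's chi-square for reconstructive failure, or Fisher's exact if counts are sparse, and limit the t/Wilcoxon sentence to the continuous secondary endpoints.
2. Report failures per arm and the risk difference with a 95% CI (for example Newcombe), counted per woman. The unit needs stating because bilateral cases are common: the table in 3.1 shows 123 + 111 + 107 = 341 of 583 reconstructions, or 58%.
3. Replace the no-difference hypothesis with an aim to estimate the difference in failure between groups.
4. State that a non-significant result will not be reported as no difference, because the trial is not powered to exclude an increase.

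A margin justified and fixed before unblinding is optional. If one is set, its power at 64 per arm should be given.

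The cost is a few sentences, with no added patients or data. The price is a less favourable conclusion: the report would probably have to say that an increase in expander loss was not excluded.
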